- This randomized controlled trial aims to determine whether awareness of personal genetic information related to obesity improves weight management outcomes among overweight and obese individuals.
- Eating habits are typically formed over a long period and are difficult to modify without a strong motivator (e.g., a medical diagnosis). However, given the symbolic and personalized nature of genetic information, awareness of one's genetic profile may serve as a powerful trigger for behavioral change. Therefore, individuals who receive their genetic results accompanied by genotype-tailored recommendations are expected to demonstrate greater improvements in weight and related indicators compared with those who do not. Specifically, the study seeks to identify characteristics of individuals who voluntarily modify their diet or lifestyle after learning about their genetic information and tailored lifestyle recommendations, and to examine subsequent changes in obesity and health indicators. If participants' habits shift toward a genetically tailored lifestyle, such personalized approaches are expected to reduce physiological stress, enhance adherence, and yield sustainable improvements in weight and metabolic outcomes.

3. Design

● Randomized Controlled Trial:

- **Subjects:** 53 overweight or obese young adults.
- **Randomization:** Participants were randomly assigned to two groups (experimental and control) using a computer-generated randomization sequence.
- **Experimental group (27 participants):** Participants received their obesity-related genetic test results (including *FTO*, *MC4R*, and *BDNF*) along with genotype-tailored lifestyle recommendations encouraging healthy behaviors such as reducing fat intake, limiting snacking, and avoiding emotional eating.
- **Control group (26 participants):** Participants received genetic test results limited to non-obesity-related traits (e.g., beauty-related genes). No lifestyle recommendations were provided. Obesity-related genetic results were disclosed only after completion of the final follow-up.
- **Follow-up:** Questionnaire surveys and body composition measurements were conducted at baseline, approximately 5 months after randomization, and at study completion (up to 17 months).

- **Inclusion Criteria:**

1. Korean adults aged 18 and older who are interested in weight management through dietary/exercise therapy.
2. Individuals who can participate consistently in the study for 2 years.

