- **Exclusion Criteria:**

1. Individuals currently suffering from illnesses requiring regular treatment in a hospital.
2. Individuals currently taking long-term prescribed medications.
3. Individuals diagnosed with an eating disorder or mental illness (e.g., depression, panic disorder) by a physician.
4. Individuals who have undergone gastric surgery for weight loss.
5. Individuals who have undergone heart surgery or cancer surgery.
6. Individuals suffering from severe anemia.
7. Individuals who are unable to exercise.
8. Pregnant or breastfeeding women, and women planning to become pregnant within 2 years.

4. Outcome assessment Method

- **Single Gene Variant Testing**

- We will evaluate single-nucleotide polymorphisms (SNPs) that may influence weight control. Key examples include genes related to energy metabolism (FTO), muscle strength (INSIG2), mood (BDNF), and taste perception (TAS2R38). Knowledge of such variants may help identify dietary and behavioral strategies that are more compatible with individual metabolic characteristics. For example, for the well-known obesity gene FTO, if a single gene variant such as rs9939609 is present, excess calories may be stored more readily as fat, making a low-calorie or low-fat diet more effective for weight control.

- **Obesity and Body Composition Measurements**

- We will assess various obesity-related parameters as follows:
 - ✓ **Body Weight Change:** The primary outcome, assessed at baseline, approximately 5 months after randomization, and at study completion (up to 17 months).
 - ✓ **Body Composition Change:** Body fat mass, body fat percentage, and skeletal muscle mass were assessed using a bioelectrical impedance analyzer (InBody720, Seoul, Korea). These secondary outcomes were measured at baseline, approximately 5 months after randomization, and at study completion (up to 17 months).

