Title: Personalized Lifestyle Intervention and Weight Control ID:

2018-12-006

NCT04079972

Proposal and Statistical analysis

In this study, we aim to conduct the most efficient analysis possible with limited research funding through appropriate epidemiological research designs and statistical analysis techniques.

1. Randomized Controlled Trial:

- **Subjects:** 53 overweight or obese young adults.
- **Randomization:** Participants were randomly assigned to two groups (experimental and control) using a computer-generated randomization sequence.
- **Experimental group (27 participants):** Participants received their obesity-related genetic test results (including *FTO*, *MC4R*, and *BDNF*) along with genotype-tailored lifestyle recommendations encouraging healthy behaviors such as reducing fat intake, limiting snacking, and avoiding emotional eating.
- **Control group (26 participants):** Participants received genetic test results limited to non-obesity-related traits (e.g., beauty-related genes). No lifestyle recommendations were provided. Obesity-related genetic results were disclosed only after completion of the final follow-up.
- **Follow-up:** Questionnaire surveys and body composition measurements were conducted at baseline, approximately 5 months after randomization, and at study completion (up to 17 months).
- **First Statistical Analysis (Intention to Treat Analysis):**
 - **Causal variable:** Knowledge of obesity-related genetic test results.
 - **Outcome variable:** Changes in body weight and body composition (body fat mass, body fat percentage, and skeletal muscle mass) compared to baseline.
 - **Statistical analysis to observe the correlation between causal and outcome variables:** The association between the causal and outcome variables will be examined using general linear regression and linear mixed models adjusted for baseline body mass index (BMI), physical activity, smoking status, and alcohol consumption.

- **Second Statistical Analysis (As Treated Analysis):**

- Although all participants in the experimental group received obesity-related genetic results and tailored lifestyle recommendations, adherence levels may vary. We will compare characteristics of those who reported behavioral changes after reading their genetic test results (“behavior changers”) with those who did not (“behavior maintainers”).

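### The intention-to-treat models adjust for baseline BMI but not for each outcome's own measured baseline: a minor, optional efficiency point, mainly for body composition

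*SAP*

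**What the plan says.** In the SAP's First Statistical Analysis (intention to treat), the outcome variable is "Changes in body weight and body composition (body fat mass, body fat percentage, and skeletal muscle mass) compared to baseline". The method follows: "The association between the causal and outcome variables will be examined using general linear regression and linear mixed models", which are "adjusted for baseline body mass index (BMI), physical activity, smoking status, and alcohol consumption". One covariate list therefore serves four outcomes, and BMI is its only anthropometric term.

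The own baselines exist. Protocol section 4 describes body weight as "The primary outcome, assessed at baseline, approximately 5 months after randomization, and at study completion (up to 17 months", and says of fat mass, fat percentage and skeletal muscle mass: "These secondary outcomes were measured at baseline, approximately 5 months after randomization, and at study completion (up to 17 months".

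The SAP names both model types. It does not say which is primary, or whether the mixed model takes change scores or raw values including the baseline visit as its response. Neither document gives an SD, a correlation, a dropout rate or a power calculation.

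**The concern.** When change is the response, the natural anthropometric covariate is the outcome's own baseline. BMI stands in for it. The worse the stand-in, the more baseline variation stays in the residual and the wider the confidence interval.

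BMI is probably a good proxy for weight. It may be a weaker one for fat percentage and muscle mass, the more so if both sexes are enrolled. The protocol's inclusion criteria do not restrict sex ("Korean adults aged 18 and older who are interested in weight management through dietary/exercise therapy"), and women are excluded only in specific circumstances ("Pregnant or breastfeeding women, and women planning to become pregnant within 2 years").

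At stake is some precision in a trial of 27 against 26 participants, whose SAP opens by aiming for efficiency on a limited budget.

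**Working it through.** The plan has no precision or power figure to reproduce. The check compares the residual variance of change under the two adjustments.

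**Inputs from the documents.** 27 and 26 participants (SAP, section 1); four planned covariates.

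**Assumed inputs.** rho = correlation of baseline with follow-up; r = correlation of BMI with own baseline; s = follow-up SD divided by baseline SD, equal to 1 unless stated. None is in the documents.

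**Step 1: BMI relates to follow-up only through own baseline.** With baseline SD 1:
- Residual variance with own baseline: s²(1 − rho²).
- Residual variance with BMI: 1 + s² − 2·s·rho − r²(1 − rho·s)².
- Ratio, BMI to own baseline: 1 + (1 − rho·s)²(1 − r²) / [s²(1 − rho²)].
- Variance cut from switching: 1 − 1/ratio.

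Example, rho 0.9, r 0.8, s 1: 1 + 0.01 × 0.36 / 0.19 = 1.019, a cut of 1.9%, worth 53 × 0.019 = 1.0 participant.

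| Setting (s = 1) | rho | r | Ratio | Variance cut |
|---|---|---|---|---|
| Weight | 0.98 | 0.9 | 1.002 | 0.2% |
| Weight | 0.95 | 0.8 | 1.009 | 0.9% |
| Weight | 0.9 | 0.6 | 1.034 | 3.3% |
| Body composition, close proxy | 0.95 | 0.85 | 1.007 | 0.7% |
| Body composition, weak proxy | 0.95 | 0.4 | 1.021 | 2.1% |
| Body composition, weak proxy | 0.9 | 0.2 | 1.051 | 4.8% |
| Body composition, weak proxy | 0.85 | 0.2 | 1.078 | 7.2% |
| Body composition, weak proxy | 0.8 | 0.4 | 1.093 | 8.5% |
| Body composition, weak proxy | 0.7 | 0.2 | 1.169 | 14.5% |
| Body composition, no proxy | 0.7 | 0 | 1.176 | 15.0% |

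Simulation of the treatment estimate (27 v 26, three further covariates, 20,000 runs per setting) agrees: 1.017 at (rho 0.9, r 0.8), 1.051 at (0.9, 0.2), 1.169 at (0.7, 0.2).

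**Step 2: the top of the range is less likely.** Stable sex differences raise rho. If the sexes are split 50:50 and lie 2 within-sex SDs apart (both assumed), overall rho = (within-sex rho + 1)/2. Within-sex values of 0.7 and 0.8 become 0.85 and 0.90, where a weak proxy costs about 4-9% extra variance.

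**Step 3: unequal SDs.** For weight at rho 0.9, r 0.8:
- s = 1.1: 1 + (0.01)² × 0.36 / (1.21 × 0.19) = 1.0002, no gain.
- s = 0.9: 1 + (0.19)² × 0.36 / (0.81 × 0.19) = 1.084, a cut of 7.8%.

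**Step 4: BMI predicts change beyond own baseline.** Let p be the size of the partial correlation of BMI with change given own baseline, with higher BMI going with more loss. With s = 1 the ratio becomes

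{2(1 − rho) − [(1 − rho)r + p·√((1 − rho²)(1 − r²))]²} / (1 − rho²).

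- Weight (0.95, 0.8), p = 0.1: (0.1 − 0.0587²)/0.0975 = 0.990, a 1% loss from switching. The gain is already gone at p = 0.053.
- Weight (0.9, 0.8): 0.993 at p = 0.1; the gain is gone at p = 0.076.
- At p = 0.2 both weight settings lose about 4%. The opposite sign raises the gain to about 2-5%.
- Body composition (0.8, 0.4), p = 0.2: (0.4 − 0.1900²)/0.36 = 1.011. At (0.8, 0.2): (0.4 − 0.1576²)/0.36 = 1.042. A gain remains.
- Body composition (0.9, 0.4): p = 0.1 gives (0.2 − 0.0799²)/0.19 = 1.019, but p = 0.2 gives (0.2 − 0.1199²)/0.19 = 0.977.

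**Step 5: keeping both covariates.** Going from four to five covariates, one degree of freedom each, multiplies the variance by (53 − 4 − 3)/(53 − 5 − 3) = 46/45 = 1.022. With 40 analysed it is 33/32 = 1.031; with 30, 23/22 = 1.045. In the simulation, adding own baseline to BMI for weight gave ratios of 0.986-1.014, with a loss in five of six settings.

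**Step 6: chance imbalance.** A 1-SE baseline imbalance left after BMI shifts the estimate by (1 − rho) × √(1/27 + 1/26) × √(1 − r²). At (0.9, 0.8) this is 0.1 × 0.275 × 0.6 = 0.0165 SD. The SE is 0.275 × √(0.2 − 0.0064) = 0.121 SD. The share is 0.0165/0.121 = 0.136, and 0.136² = 0.0186, the same 1.9% as in step 1.

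**The case against.** The strongest reply is that nothing here would change a conclusion. The planned estimate is unbiased, the primary outcome gains at most a few percent of variance, and the larger figures belong to secondary outcomes under correlations that nobody has stated. That stands, and it sets the severity.

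The mixed model may also deal with the point already. If the baseline visit is part of the response and the arms share a baseline mean, own baseline is used. In a 6,000-run check such a model matched own-baseline regression closely (1.015 against 1.016 at rho 0.9, r 0.8). The SAP is silent on this, so the point is certain only for the general linear regression.

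Three stronger readings are tempting, and the documents do not support them:
- *The change analysis is biased or invalid without own baseline.* Both documents describe random allocation by a computer-generated sequence. Adjustment for a different baseline variable does not bias the comparison.
- *Switching is a free gain for the primary outcome.* It costs no data, and no degree of freedom if BMI is dropped. But step 4 shows that for weight even the direction depends on a partial correlation that the documents do not give. Adding own baseline beside BMI is about neutral or a slight loss.
- *Chance imbalance is a second harm.* Step 6 shows that it is the same quantity as the lost precision, and it should not be counted twice.

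**Conclusion.** The point holds as a minor efficiency note. The covariate list omits each outcome's own baseline, which is measured.

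- Fat percentage, skeletal muscle mass and possibly fat mass: switching would cut variance by roughly 1-15%. A few percent is most plausible, and the top needs rho near 0.7 with a weak BMI proxy. The gain survives a partial correlation of 0.2 at rho 0.8, but not at rho 0.9.
- Weight: about 0-3% with equal SDs and about 0-8% if the SDs differ by 10%. It may be nil, or a loss of about 1% or more, if BMI predicts change beyond baseline weight.

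Every correlation and SD ratio is an assumption. Severity is low and the change is optional.

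**What to change.** In the general linear regression, and in the mixed model if its response is change from baseline, adjust each outcome for its own baseline value in place of BMI. Do this chiefly for the body composition outcomes; for weight it is optional and roughly neutral.

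State what the mixed model's response is. If it includes the baseline visit with a common mean across arms, leave that model as it is.

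Cost: no new data, and one SAP sentence if outcomes are unseen. Replacing BMI uses no extra degree of freedom; keeping both uses one, about 2% of variance at 53 participants and more with dropout. The SAP describes the measurements in the past tense ("Questionnaire surveys and body composition measurements were conducted at baseline, approximately 5 months after randomization, and at study completion (up to 17 months"). If outcome data have been seen, keep the planned BMI-adjusted model and report the own-baseline model beside it as a disclosed supplementary analysis.
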